
Evaluate initial TASS outcome (for participants deemed “OK to Use” or those with an “Ask a Doctor” outcome who contact a doctor and are permitted to continue treatment) compared to the TASS outcome obtained using clinician-verified medical and laboratory dataEvaluate that participants are properly using nonprescription rosuvastatin during the use period as assessed by their ability to correctly enter their ongoing health status into the Web App to get the correct TASS outcome or through the medical and medication history in those participants who fail to complete a final TASS use assessmentEffectiveness in lowering LDL-C in participants regardless of final use outcome	
Percentage of participants with an Overall Correct (correct + mitigated) Initial TASS Outcome at the initial self-selection (Threshold: 85% lower bound [LB])Percentage of participants with an Overall Correct (correct + mitigated) Final Use Outcome at the final use assessment (Threshold: 85% lower bound [LB])Percent change from baseline in verified LDL-C to Visit 2 (Threshold: -15% upper bound [UB], -20% point estimate)
Secondary	

Compliance with cholesterol retesting within 6 monthsCompliance with “Stop Use” warningsCompliance with “Do Not Use” warnings	
Cholesterol retest within 6 months of starting medication (that was verified at Visit 2, not including study mandated tests) by at least 60% of participants who are eligible for continuous treatmentPercentage of participants who correctly self-identify as having a “Stop Use” warning and stop medicationPercentage of participants who correctly self-identify as having a “Do Not Use” warning at the final use assessment

Objectives	Endpoints

 • Compliance with “Ask a Doctor Before Use” warnings 	
 • Percentage of participants who correctly self- identify as having an “Ask a Doctor Before Use” warning at the final use assessment

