The third co-primary endpoint was selected to evaluate the LDL-C efficacy of rosuvastatin 5 mg. Efficacy in lowering LDL-C will be evaluated as mean percent change from baseline in verified LDL-C at Visit 2. For the purposes of the statistical evaluation of this endpoint, the upper bound of the 95% confidence interval on the mean percent change from baseline (PCFB) in the overall analysis needs to be less than -15% and the point estimate needs to be less than or equal to -20%. These thresholds were chosen based on several factors: 1) 2018 AHA/ACC guidelines which state that in intermediate risk ($\geq 7.5\%$ to $< 20\%$ 10-year atherosclerotic cardiovascular disease [ASCVD] risk) patients, LDL-C levels need to be reduced by 30% or more, 2) real world clinical practice results show that a 20% or greater reduction in LDL-C is a realistic, achievable goal for 5 mg rosuvastatin in a real world setting ([Bullano et al 2006](#), [Fox et al 2007](#)) and 3) potential public health benefits for patients at increased CV risk who are not currently on any LDL-lowering therapy. Although an LDL-C lowering treatment effect of 15% to $<30\%$ is suboptimal according to the guidelines, the benefits of therapy outweigh the risks and provide an opportunity for repeated messaging to the consumer to improve their compliance with medication or to follow-up with a health care provider to optimize therapy.

The secondary endpoints were selected to evaluate compliance with retest requirements, compliance with label warnings and compliance with dosing.

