1.2 Study Design

This is a 6-month single-arm, interventional, phase III Self-Selection (SS) and Actual Use Study (AUS) using a TASS tool within a Web App. It is an open-label study using non-prescription rosuvastatin 5 mg in participants who qualify for treatment based on the medical and medication history, laboratory, and blood pressure (BP) data they enter into the Web App. A participant is considered enrolled in the study after signing the informed consent. The study will enroll

approximately 1,220 participants who will ultimately receive an “OK to Use” outcome using the Web App. Of these, an estimated 1,000 participants will ultimately be able to proceed to the use phase.

After the enrollment visit, the participant will enter a 6-month use period where they will re-purchase study drug available only through an online purchase via the Web App. Participants will be required to complete a TASS reorder assessment to confirm they are still “OK to Use” prior to re-purchase. Participants will be instructed to use an eDiary to record when they took study drug, have changes to any medications and have any changes in health status. The Central Medical Operations Group (CMOG) clinician will perform a telephone status check with participants at 60 and 120 days to assess any changes in health and/or medications as well as any additional study related issues (no instruction will be provided regarding the use of the product). A Virtual Visit 2 will be completed according to the procedures described in the Clinical Study Protocol. A 30-day follow-up phone call will be performed after study drug completion/discontinuation to assess participant status with regard to adverse events (AEs).

It is expected that a minimum of 500 evaluable participants will be assessed for the final use assessment. Evaluable means the participant completed Virtual Visit 2 or has sufficient medical and medication history information and, when necessary, a verified LDL-C collected prior to stopping the study to determine a final use outcome. The goal is to have 100 limited literacy participants in the trial.

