$$\text{PCFB} = \frac{100 * (\text{Verified LDL-C value at Visit 2} - \text{Verified LDL-C value at Baseline})}{\text{Verified LDL-C value at Baseline}}$$

where the verified LDL-C value at initial selection will serve as Baseline. The LDL-C values assessed as part of a reorder assessment and verified by the CMOG at Virtual Visit 2 will be used as the Visit 2 value. If a participant has more than one LDL-C retest during the use period, the most recent verified LDL-C value will be used in the analysis. Negative values in PCFB represent a decrease in LDL-C.

It is anticipated that at least 450 participants will be included in the evaluation of this co-primary endpoint. Assuming a true mean PCFB of -25% with a standard deviation of 25%, a sample size

of 450 participants would provide greater than 99% power to test the following set of hypotheses using a one-sample t-test at an $\alpha=0.025$ of significance:

$$H_0: \mu \geq -15\% \text{ vs. } H_1: \mu < -15\%$$

where μ is the mean PCFB in verified LDL-C to Visit 2. The above null hypothesis will be rejected in favor of the alternative if the upper bound of the two-sided 95% confidence interval on the mean PCFB in verified LDL-C to Visit 2 is less than -15%.

It is expected that approximately 80,000 consumers will contact the Call Center for pre-screening in response to advertising. Traditional (i.e., television, print) and digital advertising approaches will be utilized for recruitment. Table 1 summarizes the estimates and percentage drops at each step from the initial call into the Call Center through completion of the study.

Table 1 Estimated Number of Subjects and Participants by Study Stage

Stage	Estimates
Calls into Call Center	Estimated 80,000 calls
Sent the Web Link Assumes: Screen Fail Rate = 24% Qualified Refused Rate = 8%	Estimated 54,400 subjects
Complete the Web Link (66%)	Estimated 35,900 subjects
Qualify as "OK to Use" (~5%)	Estimated 1,800 subjects
Schedule Virtual Visit 1 (85%)	Estimated 1,525 subjects
Enrolled – Complete consent at Virtual Visit 1 (80%)	Estimated 1,220 participants
Enter Use Phase of the Study (83%)	Estimated 1,000 participants
Withdrawals/Lost-to follow-up during use (~50%)	Estimated 500 participants
Evaluable participants*	Estimated 500 participants

* Evaluable for the second co-primary endpoint, Overall Correct Final Use Outcome

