1. Best Case Scenario: All missing data assumed to be a success for the Overall Correct Final Use Outcome (i.e., participants who did not complete Virtual Visit 2 or did not provide sufficient medical history to make a final use assessment, and, therefore, have a missing final use outcome for the CMOG will be treated as Correct for the Overall Correct Final Use Outcome) (Sensitivity Analysis #1).
2. Worst Case Scenario: All missing data assumed to be a failure for the Overall Correct Final Use Outcome (i.e., participants who did not complete Virtual Visit 2 or did not provide sufficient medical history to make a final use assessment, and, therefore, have a missing final use outcome for the CMOG will be treated as Incorrect for the Overall Correct Final Use Outcome) (Sensitivity Analysis #1).
3. Tipping Point Analysis: Missing data will be imputed to identify the largest number of missing cases that could be incorrect and still yield statistically significant results, had an outcome for all missing cases been observed (Sensitivity Analysis #1).

For the third co-primary endpoint, participants in the primary LDL-C efficacy population (AUS ITT) with missing verified on-treatment LDL-C values, missing data will be imputed using various missing data imputation methods. The missing data imputation methods are as follows:

1. Best Case Scenario: All participants with missing LDL-C reduction due to missing verified LDL-C values will be treated as having a 40% reduction in LDL-C from baseline to Visit 2 (i.e., PCFB = -40%) (Sensitivity Analysis #2).
2. Worst Case Scenario: All participants with missing LDL-C reduction due to missing verified LDL-C values will be treated as having no reduction in LDL-C from baseline to Visit 2 (i.e., PCFB = 0%) (Sensitivity Analysis #2).

3. Tipping Point Analysis: Missing LDL-C reduction data due to missing verified LDL-C values will be imputed over the range of 0% reduction to 40% reduction (i.e., assuming that all participants with missing data had the same reduction in LDL-C ranging from 0% to 40%) and point estimates and corresponding 95% confidence intervals will be displayed graphically as a function of the assumed reduction in LDL-C. The graph will include a horizontal line corresponding to the success threshold of a 15% reduction (Sensitivity Analysis #2).

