Any missing Overall Correct Final Use Outcomes will be imputed using best case and worst case imputation. The PE of the Overall Correct Final Use Outcome will be reported, and the two-sided 95% confidence interval will be computed using exact binomial (Clopper-Pearson) methods for each of these imputation methods. For the *a priori* and post-study mitigations, the PE and the two-sided 95% confidence interval will be computed for each TASS outcome (C_S , C_{AAD} and C_R) that was mitigated on the AUS ITT population overall and by subgroups (Sensitivity Analysis #1).

LDL-C

Unless otherwise specified, all LDL-C analyses are performed using source document verified or study mandated LDL-C values.

The third co-primary endpoint is the percent change from baseline (PCFB) in verified LDL-C values to Visit 2 in participants regardless of their final use outcome. PCFB in verified LDL-C to Visit 2 is computed as follows:

$$\text{PCFB} = \frac{100 * (\text{Verified LDL-C value at Visit 2} - \text{Verified LDL-C value at Baseline})}{\text{Verified LDL-C value at Baseline}}$$

where the verified LDL-C value at initial selection will serve as Baseline. The LDL-C values assessed as part of a re-order assessment and verified by the CMOG at Virtual Visit 2 will be used as the Visit 2 value. If a participant has more than one LDL-C retest during the use period, the most recent verified LDL-C value will be used in the analysis. Negative values in PCFB represent a decrease in LDL-C.

The PCFB in verified LDL-C to Visit 2, along with the raw values for verified LDL-C at Baseline and Visit 2, values will be summarized using descriptive statistics and a two-sided 95% confidence interval on the AUS ITT population overall and by subgroups. The target threshold for this endpoint is that the upper bound of the 95% confidence interval on the mean PCFB in the overall analysis needs to be less than -15%, with a PE less than or equal to -20%. There will be no hypothesis testing of this endpoint in the subgroups.

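### The LDL-C tipping-point figure marks only the 15% bound as success and leaves out the stricter -20% point-estimate condition

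*SAP*

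**What the plan says.** The endpoint's threshold is given in two parts throughout. The Protocol synopsis has "Threshold: -15% upper bound [UB], -20% point estimate". Protocol 3.1 adds that "the point estimate needs to be less than or equal to -20" per cent. SAP 4.2.2, like Protocol 9.4.2.1, says of the upper bound that it "needs to be less than -15%, with a PE less than or equal to -20" per cent.

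The formal test is narrower. In SAP 1.3 the null is rejected "if the upper bound of the two-sided 95% confidence interval on the mean PCFB in verified LDL-C to Visit 2 is less than -15" per cent; the point estimate plays no part in it.

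For participants without a verified on-treatment LDL-C, SAP 4.1.3.2 plans a best case (40% reduction), a worst case (no reduction) and a tipping-point figure. The figure gives every missing participant one common value, "assuming that all participants with missing data had the same reduction in LDL-C ranging from 0% to 40" per cent, and plots the resulting point estimates and 95% confidence intervals. On the reference line it says: "The graph will include a horizontal line corresponding to the success threshold of a 15% reduction". No line at -20% is planned. The account of the same sensitivity analysis in SAP 4.2.2 covers only the best and worst cases and adds no rule for the point estimate.

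**The concern.** The figure labels one half of a two-part criterion as the success threshold. If the point-estimate condition were always the easier one, this would not matter. At the planned sample size it is the harder one, so there is a band of assumed values in which the interval clears the marked line and the endpoint's stated criterion is not met.

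The figure carries weight because much of the population is expected to be unobserved. SAP 1.3 states: "It is anticipated that at least 450 participants will be included in the evaluation of this co-primary endpoint". SAP 1.2 says that "an estimated 1,000 participants will ultimately be able to proceed to the use phase". Together these suggest that about 550 of 1,000 may have no verified Visit 2 value. The primary analysis uses observed data only (SAP 4.1.3). Participants who withdraw, discontinue or end with a Do Not Use outcome get no study-mandated test, because most will have been off treatment for some time (SAP 3.2.1). Low assumed reductions are therefore plausible for the missing group. The best and worst cases fix only the two ends, and this figure is the only planned display between them.

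**Working it through.** **Inputs.** Observed n = 450, mean -25%, SD 25%, null -15%, one-sided alpha 0.025 (SAP 1.3); total N = 1,000 (SAP 1.2); missing = 1,000 - 450 = 550 (derived); common assumed reduction r from 0% to 40% (SAP 4.1.3.2).

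**The plan's own figure.** SE = 25/√450 = 1.179. Noncentrality = (-25 + 15)/1.179 = -8.485 on 449 df. Power is above 0.9999, so the stated figure of more than 99% reproduces.

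**Which condition binds in the primary analysis.** With t(449) = 1.965, the upper bound equals -15% at a mean of -15 - 1.965 × 1.179 = -17.32%. A point estimate of -20% is therefore the stricter requirement.

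**The tipping-point figure.** Combine 450 observed values with 550 values fixed at -r:

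- Mean m = (450 × (-25) - 550r)/1,000 = -11.25 - 0.55r
- Sum of squares SS = 449 × 25² + 450(-25 - m)² + 550(-r - m)²
- SE = √(SS/999)/√1,000
- Upper bound = m + t(999) × SE

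Results:

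- Point-estimate condition: -11.25 - 0.55r = -20 gives r = 8.75/0.55 = 15.91%.
- Upper-bound condition: solving for -15% gives r = 8.91%, where m = -16.15%.
- Gap: 15.91 - 8.91 = 7.0 points of assumed reduction. In the combined mean this is 20 - 16.15 = 3.85 points of LDL-C change (3.85/0.55 = 7.0).
- Example, r = 12%: m = -17.85%, SD 17.97, upper bound -16.74%. The marked line is cleared and the full criterion fails.
- Worst case, r = 0: m = -11.25%, upper bound -9.95%. Both conditions fail.

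**Dependence on the number observed** (mean -25%, SD 25%, total 1,000; every row except 450 is an assumed count):

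| Observed | Upper bound reaches -15% at r = | Point estimate reaches -20% at r = | Gap |
|---|---|---|---|
| 400 | 10.13% | 16.67% | 6.5 |
| 450 | 8.91% | 15.91% | 7.0 |
| 500 | 7.45% | 15.00% | 7.6 |
| 600 | 3.42% | 12.50% | 9.1 |
| 659 | outside the plotted range | 10.34% | 10.4 |
| 700 | outside the plotted range | 8.33% | 11.6 |
| 800 | outside the plotted range | 0% | n/a |

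In the 659 and 700 rows the upper-bound crossing would need LDL-C to rise among the missing (by 0.05% and 3.25%), and the gap is measured from there. At 659 observed the upper bound at r = 0 is -15.02%, so the figure shows no crossing of its only line, yet the point-estimate condition fails below 10.3%. From 800 observed, neither condition fails in the plotted range.

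**Other inputs.** With 450 observed of 1,000, means of -22% to -30% and SDs of 20% to 30%, the gap is 6.4 to 7.5 points. With 450 observed and totals of 800 to 1,200, it runs from 8.1 down to 6.5.

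**The case against.** The line at -15% has a sound basis. It is the boundary of the formal null, and the SAP describes its tipping points for the first two co-primaries as loss of statistical significance. The figure hides nothing, because point estimates are plotted and a reader can find -20% on the axis. The SAP attaches no pass/fail rule to this sensitivity analysis and does not ask for a tipping value against -15% either. The worst case is tabulated and, at plan figures, fails both conditions. Observed counts of 659 or more lie well above the planned 450, and the gap looks smaller on the LDL-C scale (3.85 points) than on the horizontal axis (7.0).

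Most of this stands, and it limits the point to presentation of a sensitivity analysis. It does not rescue the label. SAP 4.2.2 defines the target for this endpoint in two parts, and the figure calls one part the success threshold.

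One could also note that Protocol 3.1 mentions a 90% point estimate beside the 85% bound for the first co-primary, while its figure draws only 85%. But the SAP 4.2.2 target for that endpoint is the lower bound alone, so there the marked line is the whole SAP target. For LDL-C it is half.

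**Conclusion.** The concern holds. Followed as written, the figure marks the non-binding half of the criterion and overstates robustness to missing data. At plan figures the misreading is confined to assumed reductions of about 9% to 16%. If about 659 or more of 1,000 are observed, the marked line shows no tipping point at all while the -20% condition can still fail; that case is outside the planning assumptions and is not needed for the conclusion.

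The size rests on treating the floor of 450 and the estimate of 1,000 as actual counts, and on a mean of -25% and SD of 25% among those observed. In the ranges tried with 450 observed, the gap stayed between 6.4 and 8.1 points. The formal test, its power and the primary decision rule are unaffected. The change should be made.

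**What to change.** In SAP 4.1.3.2, describe the 15% line as the threshold for the upper confidence bound and add a second line at -20% for the point estimate. Define the tipping point as the first assumed reduction, moving down from 40%, at which either condition fails, and report both crossings.

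The cost is one SAP sentence, one extra line on the figure and two reported values. No new data or tests are needed. The reported tipping point will look less favourable: about 15.9% rather than 8.9% at plan figures.

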4.2 Analysis methods

4.2.1 Analysis of Baseline Participant Characteristics and Diagnostics

For subjects who are Pre-Screen Failures:

- The categorical baseline characteristics of age group, sex at birth, education level, race, employment status, and annual household income will be summarized using frequency counts and percentages based on the data captured in the Pre-Screener. The denominator for the percentages will be the total number of subjects in the Pre-Screen Failure population overall.

Subjects can choose to complete part of the pre-screening for SS eligibility criteria via an online pre-screener or call the Call Center to complete all pre-screening questions. Anyone that qualifies after completing the online pre-screener is directed to call the Call Center to complete additional pre-screening questions. Those that do not qualify are not directed to call the Call Center to complete the additional pre-screening questions.

- Subjects who choose to complete the online pre-screener and do not qualify or subjects who qualify via the online pre-screener but do not call the Call Center to answer the follow-up pre-screening questions will have incomplete prescreening data.

The baseline subject characteristics and demographics will be summarized for the Pre-Screen Failure population overall and by each pre-screen failure category as defined in [Section 2.1](#).

The Pre-Screen Failure population will be used to analyze the initial subject TASS outcome and reason for outcome in women under the age of 50 years old. The subject TASS entries entered by women under the age of 50 years old will be listed.

Recruitment by geographic region, based on the U.S. Census Bureau, and state for the individuals who were sent a TASS link for the pre-screen eligible and registered population will be presented. The corresponding information for the SS population is also presented.

For all participants in the SS population:

- The categorical baseline characteristics of education level, employment status, and household income will be summarized using frequency counts and percentages based on the

data captured in the Pre-Screener. The categorical baseline characteristics of sex at birth, age, and race will be summarized using frequency counts and percentages based on the data captured in the Targeted Medical and Medication History Form at Visit 1. The denominator for the percentages will be the total number of participants in the SS population. This analysis will be repeated by subgroups as defined in [Section 4.1.2](#).

- For the initial TASS assessment entered by the participant:
 - The continuous baseline characteristics (age) and diagnostics (TC, HDL-C, LDL-C, TG, SBP, DBP, hs-CRP, CAC and waist circumference) will be summarized using descriptive statistics overall and by subgroup based on the data captured in the TASS tool at the initial assessment.
- For the initial TASS assessment entered by the CMOG:
 - The continuous diagnostics (TC, HDL-C, LDL-C, TG, SBP, DBP, hs-CRP, CAC and waist circumference) will be summarized using descriptive statistics overall and by subgroup based on the data captured in the Diagnostic Report Visit 1 iCRF. The continuous baseline characteristic of age will be summarized using descriptive statistics based on the data captured in the Targeted Medical and Medication History Form at Visit 1, which is the same value the CMOG clinician will enter into the TASS tool. REALM score is gathered from the results of the REALM test and will be summarized overall and by subgroup using descriptive statistics.
 - The SILS2 question will be used to estimate the percentage of limited literacy participants enrolled in the sub-study. The SILS2 asks, “How confident are you filling out medical forms by yourself?” Participants can respond “extremely,” “quite a bit,” “somewhat,” “a little bit,” or “not at all.”
 - The SILS2 and REALM data collected in this study will be evaluated in the SS Population to determine the optimal SILS2 threshold for the classification of participants as limited literacy or normal literacy in the sub-study. The screening question, “How confident are you filling out forms by yourself?” (SILS2) will be scored by assigning the values 0, 1, 2, 3, and 4 to the five possible responses to the question, where 0 represents extreme confidence and 4 represents no confidence in independently filling out medical forms. These numerical responses will be compared to the REALM classifications of limited literacy and normal literacy to produce a Receiver Operator Characteristic (ROC) curve. The area under the ROC curve (AUC) will also be provided. Values of sensitivity and specificity will be computed for each SILS2 threshold ($\leq 0, \leq 1, \leq 2, \leq 3, \leq 4$).

The analysis completed for the SS population will be repeated for those participants in the AUS ITT and PP populations.

Disease background and characteristics based on the targeted medical and medication history form will be presented for the SS population overall and by subgroups as well as the AUS ITT and PP populations.

The participant's order preference of the investigational product in increments of 45-day supply, 90-day supply, or mix (started 45d then switched to 90d, or vice versa) will be tabulated by number and percentage.

Additionally, the number and percentage of participants with a verified source for their diagnostic data at Virtual Visit 1 will be summarized overall and by subgroups for each diagnostic variable and source (e.g., doctor/prescription, home test kit, etc.) for those participants in the SS, AUS ITT, and PP populations.

A detailed listing of baseline characteristics and diagnostic data for each participant will also be provided as shown.

